8.1 EFFICACY ASSESSMENTS

Participants will undergo tumor assessments as designated in the SOA (see [Section 1.3](#)) regardless of dose delays, until loss of clinical benefit as determined by the Investigator (unless the participant withdraws consent, or the Sponsor terminates the study). All participants who discontinue study intervention for reasons other than disease progression (eg, AEs) will continue tumor assessments for up to 2.5 years from initiation of study intervention or until study completion, death, disease progression, loss to follow-up, withdrawal of consent, or study termination, whichever occurs first. At the Investigator's discretion, tumor assessments may be repeated at any time if PD is suspected.

Measurable and evaluable lesions should be assessed and documented at screening. Tumor assessments performed as standard of care prior to obtaining informed consent and within 28 days prior to the first dose of study intervention do not have to be repeated at screening.

Screening assessments must include computerized tomography (CT) scans (with IV contrast unless contraindicated and oral contrast as appropriate per institutional standards) of the chest, abdomen, and pelvis. A spiral CT scan of the chest may be obtained but is not a requirement. If a CT scan with contrast is contraindicated (ie, in participants with contrast allergy or impaired renal clearance), a non-contrast CT scan of the chest maybe performed and magnetic resonance imaging (MRI) scans of the abdomen and pelvis should be performed. If the participant has a known history of brain metastases or is symptomatic in the opinion of the Investigator, scans of the head should be obtained.

If a CT scan for a tumor assessment is performed in a positron emission tomography (PET)/CT scanner, the CT acquisition must be consistent with the standards for a full contrast diagnostic CT scan.

Bone scans (technetium-99m [TC-99m]) should be performed at screening if clinically indicated. If bone metastases are present at screening and cannot be seen on CT or MRI scans, or if clinically indicated, TC-99m bone scans should be repeated when complete response (CR) is identified in target disease or when progression in bone is suspected.

CT scans of the neck or extremities should also be performed if clinically indicated and repeated throughout the study if there is evidence of disease at screening.

All measurable and evaluable lesions should be reassessed at each subsequent tumor evaluation. The same radiographic procedures used to assess disease sites at screening should be used for subsequent tumor assessments (eg, same contrast protocol for CT scans).

Response will be assessed by the Investigator using PCWG3-modified RECIST 1.1 (see [Appendix 3](#)). Assessments should be performed by the same evaluator, if possible, to ensure internal consistency across visits. Results must be reviewed by the Investigator before dosing at the next cycle.

Radiographic confirmation of disease progression is required by repeat scans 4 – 6 weeks following any scan suggesting disease progression. Participants will remain on study and continue to receive study intervention during this time.

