The duration of immunotherapy combination study intervention will be dependent on the combination administered and will continue for the duration described in the cohort appendix for each respective combination, unless the participant: is no longer clinically benefiting (NLCB; as

evidenced by symptomatic or radiographic disease progression and/or clinical deterioration); experiences any toxicity meeting specified discontinuation criteria (as described in the cohort appendix for each respective combination) or unacceptable toxicity in the best clinical discretion of the treating physician (ie, Investigator discretion); reaches the maximum duration of study intervention; or withdraws consent. Participants will be followed for up to 2.5 years from the time of the initiation of study intervention (see Follow-up). Depending on the combination administered, participants who are clinically benefiting, as defined by the Investigator at the end of the study treatment period, may have post-study access to the immunotherapy combination received during the study after written agreement from the Medical Monitor.

Number of Participants:

The study is not intended or powered for hypothesis testing. The study is intended to provide preliminary estimates of adverse event (AE) rates, response rates, effect sizes, and confidence intervals (CIs) to aid the design of later studies. A sample size of approximately 15 participants per combination intervention will provide these preliminary estimates while limiting exposure. An additional approximately 15 participants will be enrolled in Stage 2, if the cohort is expanded.

Intervention Groups and Duration:

This is not a randomized study. Assignment to one of the immunotherapy combinations will be made by the Investigator using his/her best clinical discretion based on the participant's medical history and disease status and knowledge of the available immunotherapy combinations open for enrollment.

The dose and schedule selected will be described in the cohort appendix for each respective combination (eg, Appendix Cohort A, Appendix Cohort B, etc.). The duration of immunotherapy combination study intervention will be dependent on the combination administered. Depending on the combination administered, participants who are clinically benefiting as defined by the Investigator at the end of the study may have post-study access to the immunotherapy combination after agreement from the Medical Monitor.

Follow-up:

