Radiographic disease assessment	X	Per PCWG3 guidelines: Every 8 to 9 weeks (± 1 week) for first 24 weeks, and every 12 weeks (± 1 week) thereafter until radiographic PD or start of subsequent therapy. Refer to the cohort appendix for each respective combination for cohort-specific details							
Review of alternate anticancer therapy ^o								X	X
Follow-up for overall survival								X	X

ADA = anti-drug antibodies; AE(s) = adverse event(s); AESI(s) = adverse event(s) of special interest; cfDNA = cell-free deoxyribonucleic acid; ECG = electrocardiogram; ECOG = Eastern Cooperative Oncology Group; EOT = end of treatment; I/E = inclusion/exclusion; PCWG3 = Prostate Cancer Clinical Trials Working Group 3; PD = progressive disease; PD-1 = programmed cell death 1; PK = pharmacokinetics; Q3M = every 3 months; SAE(s) = serious adverse event(s)

^a Tests/procedures performed as standard of care prior to obtaining informed consent and within 28 days prior to the first day of study intervention administration do not have to be repeated at screening.

^b The End of Treatment Visit will be completed following the last dose of study intervention, either at completion of the on-treatment phase or at early discontinuation.

^c For up to 2.5 years from the initiation of study intervention, participants in the follow up phase will be contacted by the site to collect alternate anticancer therapy information and determine survival status.

^d Informed consent must be obtained prior to any study-specific procedures and may be obtained prior to the 28-day screening window.

^e Body weight may be required more frequently for study interventions using weight-based dosing. Combination-specific frequency will be provided in the cohort appendix for each respective combination.

^f Blood samples should be collected prior to administration of any study intervention.

^g 12-Lead ECG will be collected at screening, Cycle 2 and Cycle 4.

^h Circulating tumor cells will be collected at baseline (ie, Day 1 of Cycle 1 prior to study intervention administration), Day 1 of each cycle (prior to study intervention administration), and EOT.

ⁱ cfDNA (blood) will be collected at baseline (ie, screening visit prior to study intervention administration), Day 1 of Cycle 2 and Cycle 4, and EOT.

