5.4.2.3 Radiographic Progression-Free Survival

rPFS is defined as the time from initiation of study intervention to the first objective evidence of radiographic progression or death due to any cause (whichever occurs first). Radiographic disease progression is defined as soft tissue (non-bone) disease progression per RECIST v1.1 or confirmed progression of bone disease per PCWG3 criteria. Participants who continue treatment beyond initial disease progression will be considered to have progression of disease (PD) at the time of the initial progression event.

Participants who do not have radiographic PD at the time of analysis will be censored as follows:

- Participants who do not have radiographic PD and are still on study at the time of analysis will be censored at the date of the last tumor assessment documenting absence of progressive disease
- Participants who have discontinued study treatment and have started subsequent anti-cancer therapy or had subsequent cancer surgery or radiation prior to documentation of radiographic PD will be censored at the date of the last evaluable tumor assessment prior to the initiation of subsequent treatment.
- Participants who discontinued the study prior to documentation of radiographic PD will be censored at the date of the last tumor assessment documenting absence of progressive disease.
- Participants who do not have radiographic PD and who die more than 16 weeks from their last evaluable tumor assessment will be censored at the date of the last tumor assessment documenting absence of progressive disease. Participants who within 16 weeks of their last evaluable tumor assessment will be considered as having an event at the date of death.

rPFS will be estimated using Kaplan-Meier techniques, and the median survival time and 95% CIs will be estimated within each cohort. If median survival is not reached, survival times and 95% CIs will be reported at deciles that are estimable given the observed events.

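### Protocol 8.1 and Table 1 end tumour imaging at different points, and under the SAP's censoring rules the 8.1 rule is likely to bias rPFS upward

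*Protocol*

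**What the plan says.** **Protocol 8.1** opens with a link to the schedule: "Participants will undergo tumor assessments as designated in the SOA". The same sentence then sets its own end point, "until loss of clinical benefit as determined by the Investigator". The next sentence provides for continued scanning, but for a limited group: "All participants who discontinue study intervention for reasons other than disease progression (eg, AEs) will continue tumor assessments".

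**Protocol 1.3, Table 1** gives the imaging interval as "Every 8 to 9 weeks (± 1 week) for first 24 weeks, and every 12 weeks (± 1 week) thereafter" and ends it differently, "until radiographic PD or start of subsequent therapy".

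**Protocol 1.1 (Synopsis)** describes loss of clinical benefit as "evidenced by symptomatic or radiographic disease progression and/or clinical deterioration". It can therefore be declared without radiographic PD. **Protocol 7.1** lists symptomatic deterioration attributed to progression, and unequivocal symptomatic progression, among the reasons to stop treatment. It closes by referring all participants to the SOA for follow-up.

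**SAP 5.4.2.3** recognises two rPFS events, radiographic progression and death. Those still on study without PD are censored at the last scan showing no PD. The same date applies to those who leave: "Participants who discontinued the study prior to documentation of radiographic PD will be censored" there too. Those who start new treatment are censored at the last evaluable scan before it. A death more than 16 weeks after the last scan is censored; within 16 weeks it is an event (that sentence lacks its verb, and I read it as referring to deaths). Clinical progression is not an event, and no sensitivity analysis is given.

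**The concern.** The two imaging rules part company for one kind of participant: symptomatic progression or clinical deterioration, no radiographic PD yet, and no new anticancer therapy. Table 1 keeps scanning him. Section 8.1 stops, and its continuation sentence does not rescue him, because he stopped for disease progression.

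Once scans stop he can no longer have a radiographic event, and the SAP censors him at a scan taken before he deteriorated. Kaplan-Meier estimation then treats him as having the same outlook as those still being scanned, although he was removed because he was getting worse. The expected direction is rPFS that looks too long.

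The stated purpose of the study is to supply estimates for designing later studies. Each cohort is a single arm, so there is no comparator in which the bias could cancel. The SAP is more careful with DCR: under 5.4.2.2, stable disease last documented before 6 months does not count as disease control. No comparable protection exists for rPFS.

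**Working it through.** **1. The plan's own figures.** There is no design figure for rPFS. The only operating characteristics are those of the two-stage rule for composite response (Protocol 9.2): type I error 0.07, power 77%, early termination 55%. The exact calculation sums, over x ≥ 2, P(Bin(15, p) = x) × P(Bin(15, p) ≥ 6 − x). It gives 0.0684 at p = 0.10 and 0.774 at p = 0.25; early termination, P(Bin(15, 0.10) ≤ 1), is 0.549. All three reproduce, but none bears on rPFS.

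**2. One participant under each rule.** Take scans at weeks 8, 16, 24 and 36, symptomatic progression at week 20, and radiographic PD that would be visible at week 24.

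- *Table 1, no new therapy:* scanned at week 24; event at week 24.
- *Section 8.1, no new therapy:* last scan at week 16; censored at week 16 unless he dies by week 16 + 16 = 32.
- *New therapy at week 22:* Table 1 also stops before week 24, and the SAP censors at week 16 under either rule.

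The conflict therefore matters only when new therapy is absent or delayed.

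**3. Size under assumed inputs.** The documents give no rPFS rate, no rate of clinical failure before radiographic PD and no rate of subsequent therapy. A simulation of 20,000 participants per scenario used these assumptions:

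- scans at weeks 8, 16 and 24, then every 12 weeks, with a 130-week horizon;
- exponential time to first failure, median 24 weeks;
- 10% to 40% failing clinically before radiographic PD, with PD following on average 8 weeks later;
- median 40 weeks from failure to death;
- none, half or all of those failing clinically starting new therapy, 4 or 12 weeks after failure.

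The SAP 5.4.2.3 censoring rules were applied. Selected results for 26-week rPFS:

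| Fail clinically first | Start new therapy | 8.1 | Table 1 | Difference (points) |
|---|---|---|---|---|
| 10% | none | 0.52 | 0.51 | 1 |
| 20% | none | 0.55 | 0.52 | 3 |
| 30% | none | 0.59 | 0.54 | 5 |
| 40% | none | 0.62 | 0.54 | 8 |
| 30% | half, at 4 weeks | 0.59 | 0.56 | 3 |
| 30% | all, at 12 weeks | 0.59 | 0.55 | 4 |
| 30% | all, at 4 weeks | 0.59 | 0.59 | 0 |
| 40% | all, at 4 weeks | 0.63 | 0.63 | 0 |

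To two decimals, no scenario run showed a downward shift. The Kaplan-Meier median moved by 0 to about 4 weeks (largest: 43.43 − 39.27 = 4.16). In most scenarios it was 36 weeks under both rules, which is a scan date.

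**4. What the wording change alone would do.** Among participants failing clinically, 82% to 94% were censored under 8.1. Under Table 1 the figure ran from 3% (no new therapy) to 86% (all starting at 4 weeks). Adopting Table 1 therefore helps only where new therapy is absent or late.

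**The case against.** **The 8.1 wording has a natural purpose.** Protocol 4.4 allows treatment beyond radiographic PD, so scans must run past the first PD until benefit is lost. For those participants rPFS is unaffected, because the SAP dates PD at the initial event. This stands for that group, but the wording is not confined to it.

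**The schedule is invoked twice.** Section 8.1 cites the SOA and 7.1 sends everyone to it. That suggests the Table 1 rule was intended. It does not settle the matter, because 8.1 adds a different end point in the same sentence.

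**Symptomatic-only progression should be uncommon.** Protocol 10.5.5 calls it rare and asks that progression be documented objectively, and 8.1 permits extra scans when PD is suspected. This limits the size: at 10% the shift is about 1 point. Stopping scans early also works against that same request.

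**The cohort appendices may govern.** Protocol 1.3 lets them supersede the general schedule, and they are not among the documents. The core text still conflicts.

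**Materiality is modest.** rPFS is secondary and descriptive, and expansion uses composite response. As a scale for sampling error, the plan's exact 95% interval at an observed 40% has a half-width of (67.7 − 16.3)/2 = 25.7 points at n = 15 and (59.4 − 22.7)/2 = 18.35 at n = 30. This stands; the bias is smaller than the noise, though systematic and avoidable.

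**Stronger readings are not supported.** A reader might infer that rPFS is overstated by a known amount, or that every clinically failing participant is censored. The documents supply no inputs for an amount. Deaths within 16 weeks of the last scan are events, and loss of benefit at or after radiographic PD is already counted. Nor do the documents show that sites have in fact followed different sections.

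**Conclusion.** The contradiction between Protocol 8.1 and Table 1 is real and should be reconciled. Following 8.1 makes censoring depend on worsening disease in participants with symptomatic progression, no radiographic PD and no new therapy, so rPFS is likely biased upward.

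The direction rests on the reasoning above and was not reversed in any scenario run. The size is not established: about 0 to 8 points at 26 weeks is a range over assumed inputs. It is near zero when new therapy starts promptly or when symptomatic-only progression is as rare as Protocol 10.5.5 suggests. The 26-week point is relevant because SAP 3.4 sets the primary analysis after at least 6 months of follow-up.

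The point does not touch the primary safety endpoint, the composite response or the expansion decision. It is worth correcting because the remedy is cheap and the endpoint is a named secondary one.

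**What to change.** 1. **Protocol 8.1 and Table 1: one imaging rule for the endpoint.** State in both places that scans continue after study treatment stops for any reason, including symptomatic progression, until radiographic PD, subsequent anticancer therapy, death or withdrawal. Keep the confirmatory scans after suspected progression in 8.1 and the assessments needed for treatment beyond progression in 4.4; copying the Table 1 line unchanged would not secure either. Check the cohort appendices for the same conflict. This concerns endpoint ascertainment only, not when treatment should stop.

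2. **SAP 5.4.2.3: one sensitivity analysis.** Count as rPFS events both discontinuation for clinical or symptomatic progression without radiographic PD and start of subsequent anticancer therapy, and define the event date for each. Report it beside the main analysis. This part is essential, because step 1 leaves the censoring at new therapy in place and cannot help participants whose scans have already stopped.

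**Cost.** The scans are already in Table 1. The reason for stopping treatment (Protocol 7.1, summarised under SAP 5.2) and new anticancer therapy (Protocol 7.2) are already collected. SAP section 6 already foresees a Core Protocol amendment for endpoint differences, which could carry the wording. The price is one extra analysis and rPFS that may look slightly shorter. The expansion rule is unaffected.

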4.4 TREATMENT BEYOND DISEASE PROGRESSION

Accumulating evidence indicates that a minority of patients treated with immunotherapy may derive clinical benefit from continued treatment despite initial evidence of disease progression ([Wolchok et al., 2009](#)). The PCWG3 introduced the concept of treatment beyond progression (where clinical benefit by one or more disease manifestations is being observed) as clinical measure for outcome in prostate cancer ([Scher et al., 2016](#)). The PCWG3 recommendation included a reporting metric of no longer clinically benefiting (NLCB), defined as the date and specific reason(s) therapy was ultimately discontinued, to allow individualized provider-patient decisions to discontinue or continue treatment.

Therefore, participants receiving immunotherapy combinations in this study will be permitted to continue study intervention beyond initial Investigator-assessed disease progression (according to PCWG3-modified RECIST 1.1) provided all of the following criteria are met:

- Absence of symptoms and signs indicating rapid disease progression, including decline in performance status, and confirmation of disease status required

- Absence of progressive tumor at critical anatomical sites (eg, cord compression) requiring urgent alternative medical intervention
- Participant is adequately consented regarding the potential risks of continuation of ineffective therapy/failure to initiate effective alternative therapy, if any
- Written agreement from the Medical Monitor.

The assessment of clinical benefit should consider whether the participant is clinically deteriorating and unlikely to receive further benefit from continued treatment.

All decisions to continue treatment beyond initial progression must be discussed with the Medical Monitor and written agreement from the Medical Monitor should be documented in the study records.

Participants should discontinue study intervention upon evidence of further progression, defined as an additional $\geq 10\%$ increase in tumor burden from the time of initial progression (including all target lesions and new measurable lesions, or unequivocal progression of non-target lesions).

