7 DISCONTINUATIONS OF STUDY INTERVENTION AND PARTICIPANT DISCONTINUATION/WITHDRAWAL

7.1 DISCONTINUATION OF STUDY INTERVENTION

Participants must discontinue study intervention if they experience any of the following:

- Intolerable toxicity related to study intervention, including the development of an adverse event (AE) determined by the Investigator to be unacceptable even with the participant's potential response to intervention due to the severity of the event
- Any medical condition that may jeopardize participant safety if he continues to receive the study intervention
- Use of another anticancer therapy (see [Section 6.5.2](#) and as described in the cohort appendix for each respective combination, as applicable)
- Symptomatic deterioration attributed to disease progression

- Progression of disease: Either unequivocal symptomatic progression necessitating a change in therapy in the opinion of the treating physician or confirmed radiographic progression as defined by cross-sectional imaging per PCWG3-modified RECIST 1.1 (see [Appendix 3](#)) in the absence of clinical benefit (refer to [Section 4.4](#)).

Participants have the right to voluntarily withdraw from study intervention at any time for any reason. In addition, the Investigator has the right to withdraw a participant from study intervention at any time. Reasons for withdrawal from the study intervention may include, but are not limited to, the following:

- Investigator or Sponsor determines it is in the best interest of the participant
- Participant noncompliance

The primary reason for study intervention discontinuation should be documented on the appropriate eCRF page.

The visit at which disease assessment shows progressive disease (PD) may be used as the treatment discontinuation visit if it occurs within 28 (± 7) days after the last dose of study intervention. Participants who discontinue study intervention for any reason other than PD or loss of clinical benefit should have an end of treatment discontinuation assessment as outlined in the SOA (see [Section 1.3](#)). All participants should continue follow-up as outlined in the SOA.

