Appendix Table 2: Response Based on Evaluation of Nontarget Lesions at Each Assessment

Complete response	Disappearance of all non-target lesions; all lymph nodes must be nonpathologic in size (ie, < 10 mm on the short axis)
Not complete response nor progressive disease	Persistence of 1 or more non-target lesions
Progressive disease	Unequivocal progression ^a of any existing non-target lesion or the appearance of 1 or more new lesions ^b

^a The participant should stop study intervention, even in the presence of a partial response or stable disease, based on assessment of target lesions.

^b The finding of a new lesion should be unequivocal and not possibly attributable to a difference in imaging modality or scanning technique. Post-baseline, fluorodeoxyglucose positron emission tomography (FDG-PET) may be useful in assessing new lesions apparent on CT scan.

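### Protocol Sections 8.1 and 4.4 and Appendix Table 2 footnote a conflict on study treatment at first radiographic progression, and no passage supplied says which governs

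*Protocol*

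**What the plan says.** Four places in the protocol bear on study treatment when a scan first shows progression.

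- **Section 8.1 (Efficacy Assessments).** "Radiographic confirmation of disease progression is required by repeat scans" 4 to 6 weeks after any scan that suggests progression. For that interval: "Participants will remain on study and continue to receive study intervention during this time". No condition or exception is given.
- **Section 4.4 (Treatment Beyond Disease Progression).** Participants "will be permitted to continue study intervention beyond initial Investigator-assessed disease progression" "provided all of the following criteria are met". The criteria are no symptoms or signs of rapid progression, no progressive tumour at a critical site, consent to the risks of continuing, and the Medical Monitor's written agreement. It adds: "All decisions to continue treatment beyond initial progression must be discussed with the Medical Monitor".
- **Appendix Table 2, footnote a.** At unequivocal progression of a non-target lesion: "The participant should stop study intervention, even in the presence of a partial response or stable disease" on the target lesions. It mentions neither a confirmatory scan nor Section 4.4.
- **Section 7.1 (Discontinuation of Study Intervention).** Stopping is mandatory for "Symptomatic deterioration attributed to disease progression" and for unequivocal symptomatic progression that calls for a change of therapy. It is also mandatory for "confirmed radiographic progression as defined by cross-sectional imaging per PCWG3-modified RECIST 1.1" when clinical benefit is absent, and there the text refers to Section 4.4.

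**The concern.** A site with a new progression scan in hand needs one answer on the next dose. Depending on the page it opens, it finds an instruction to continue, a permission that depends on conditions, or an instruction to stop. A site that follows Section 8.1 to the letter could dose for 4 to 6 weeks without the consent discussion and written agreement that Section 4.4 requires. A site that follows footnote a would stop a participant whom Section 8.1 says should stay on treatment. Either site could be recorded as deviating from another passage of the same protocol.

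The data are touched too. The primary endpoint is the incidence and severity of adverse events, exposure is summarised as doses and cumulative dose (SAP 5.5.1), and adverse event collection is timed from the last dose (Protocol 8.3.1). All three can depend on which passage a site happened to apply.

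**Working it through.** No sample size, power or alpha figure is in dispute. The check sets the passages side by side for a participant **still on treatment** at the first scan suggesting progression.

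| Situation | 8.1 | 4.4 | Footnote a | 7.1 | Conflict? |
|---|---|---|---|---|---|
| All 4.4 criteria met, written agreement in place, no unequivocal non-target progression, no symptomatic stop | continue | may continue | not triggered | radiographic stop not yet triggered | No |
| A 4.4 criterion fails, or written agreement is missing | continue | not permitted | not triggered | not yet triggered | Yes: 8.1 against 4.4 |
| Unequivocal non-target progression, all 4.4 criteria met | continue | may continue | stop | not yet triggered | Yes: 8.1 and 4.4 against footnote a |
| Symptomatic stop in 7.1 applies | continue (no exception stated) | depends on the criteria | depends on the lesions | stop | Yes: 8.1 against 7.1 |

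**Is precedence stated?** No passage supplied ranks these instructions. The SAP says that it supersedes the protocol, but that concerns analyses, not treatment.

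**Does 7.1 conflict on its radiographic criterion?** No. It acts on confirmed progression, so it follows 8.1 in time (rescan, then decide), and it refers to 4.4. Only the symptomatic criteria in 7.1 collide with the unqualified sentence in 8.1.

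**Effect on adverse event collection.** Inputs: the repeat scan comes 4 to 6 weeks after the first (8.1), and collection lasts at least 100 days after the last dose (8.3.1). Assumption: under the stop reading, the last dose falls at about the first progression scan (day 0); under the continue reading, dosing runs to the repeat scan.

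- Stop reading: collection may end at about 0 + 100 = day 100.
- Continue reading, rescan at 4 weeks: 4 × 7 = 28, and 28 + 100 = day 128.
- Continue reading, rescan at 6 weeks: 6 × 7 = 42, and 42 + 100 = day 142.

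The difference is at most 28 to 42 days. It is an upper bound, because the actual last dose depends on cycle lengths in cohort appendices that were not available.

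**Effect on rPFS.** Protocol 9.3.1.2 and SAP 5.4.2.3 both date the event at initial progression even if treatment continues. The rPFS event date is therefore the same under each reading.

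**The case against.** The best reply is that the protocol, read as a whole, hangs together.

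- **Section 8.1 is not free of safeguards.** Section 8 allows a dose only when the clinical assessment and laboratory values are acceptable, 8.1 itself has the Investigator review results before the next cycle, and the stops in 7.1 are mandatory. This stands as protection against the worst case. It does not supply the consent and written agreement in 4.4, and it does not tell a site how to read 8.1 beside footnote a.
- **Section 4.4 might apply only after confirmation.** Its first criterion does mention confirming disease status, so it expects a repeat scan. But it speaks of initial progression and covers all decisions to continue past that point. Even if the reading is accepted, footnote a stays unresolved.
- **Footnote a belongs to the basic RECIST text, which Section 10.3.3 then modifies.** That section reports the PCWG3 shift away from stopping strictly at first progression. It summarises recommendations, though, and no sentence sets the footnote aside.
- **Cohort appendices may settle the matter.** They were not available, and the core text applies unless otherwise specified. This limits what can be said about actual site practice; it does not remove the conflict in the core text.

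Stronger readings are tempting and do not hold. A reader might infer that all four passages are mutually incompatible; the radiographic criterion in 7.1 is not. A reader might infer that every participant is affected at first progression; the first row of the table shows a group with no conflict, and participants already off treatment are not affected. A reader might treat the moving adverse event window as a flaw in itself; it is tied to last dose by design, and the issue is only that the last dose can depend on which passage is followed. A reader might also link this to the composite response rate. The absence of a cut-off at radiographic progression for CTC and PSA responses in SAP 5.4.2.1 is a separate question: as written, such responses count whichever treatment passage governs.

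**Conclusion.** The inconsistency is real. It lies between Sections 8.1 and 4.4 and Appendix Table 2 footnote a, together with the failure of 8.1 to except the symptomatic stops in 7.1. It affects participants on treatment at first radiographic progression who fall into any of the last three rows of the table. The documents do not allow an estimate of how many that is.

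The consequences are a possible difference in exposure and a shift of up to about 4 to 6 weeks in the end of adverse event collection, the latter assuming that dosing continues to the repeat scan. More important, a participant could be dosed through that interval without the consent and written agreement that another section requires. rPFS event dates are unaffected. No view is taken here on which treatment instruction is right.

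**What to change.** Reconcile Section 4.4, Section 8.1 and Appendix Table 2 footnote a into one rule for study treatment at first radiographic progression. State it once, have the other places refer to it, and cross-reference it to the mandatory stops in Section 7.1, including the symptomatic ones. The clinical content is for the sponsor's clinical team to decide. The sponsor should also check that each cohort appendix agrees with the result.

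The cost is protocol amendment wording and the usual ethics review. SAP Section 6 already foresees a Core Protocol amendment for the endpoint differences, so the text could go into the same one. Sample size, endpoints and analyses do not change.
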